## **Rationale and Background:**

Dual antiplatelet therapy (DAPT) with aspirin and clopidogrel represents the standard of care for the prevention of recurrent ischemic events in patients undergoing percutaneous coronary intervention (PCI). For more than 20 years, dual antiplatelet therapy with aspirin and Clopidogrel has remained the cornerstone of treatment for patients with acute coronary syndrome (ACS). However, some patients have impaired clopidogrel response and thus persist with high on-treatment platelet reactivity (HPR) resulting in an increased risk of atherothrombotic events. The boxed warning added to the clopidogrel label underscoring the potential risk of adverse cardiovascular outcomes among patients with a “poor metabolizer” genotype and advocating the use of other antiplatelet medications or alternative dosing strategies for these patients has led to investigations of treatment options associated with more optimal platelet inhibition. These include switching to a novel generation P2Y12 inhibitor (e.g. prasugrel or ticagrelor).

Sodium-glucose transport 2 inhibitors (SGLT2i) such as empagliflozin have been found to reduce the risk of hospitalization for heart failure and death in individuals with type 2 diabetes, although the exact mechanism behind this effect is not yet fully understood. It is also uncertain whether empagliflozin's impact on platelet function plays a role in its ability to decrease cardiovascular mortality. SGLT2i therapies have become increasingly important for T2DM patients, as evidenced by major clinical trials like EMPA-REG OUTCOME and DAPA-HF, which have shown a significant reduction in major adverse cardiovascular events (MACE). The exact mechanisms responsible for these positive cardiovascular outcomes are still being investigated. It is currently unknown whether SGLT2 inhibition has an antiplatelet effect. However, a pilot study has shown that empagliflozin does have a greater antiplatelet effect than traditional treatments for T2DM patients with coronary artery disease (CAD). This study is important for its potential to improve both efficacy and safety in the treatment of T2DM.

## **Hypothesis:**

1. Empagliflozin attenuates platelet reactivity in patients with diabetes mellitus.
2. Empagliflozin decreases platelet reactivity by 10%.

## ***Null Hypothesis:***

There is no difference in response in patients with stable coronary artery disease on DAPT concerning PRUs on Empagliflozin.

## **Study Goals and Objectives:**

1. To describe platelet function profiles of patients with stable coronary artery disease on DAPT on Empagliflozin.

## **Study Design:**

The study will be a prospective, open-label study that aims to assess the effect of empagliflozin 25 mg once daily for 10 days. Patients at the Eric Williams Medical Sciences Complex (EWMSC), Mt. Hope, Trinidad and Tobago will be screened for potential eligibility.

### **Methodology:**

#### *Inclusion criteria*

Patients will be screened and considered eligible for the study if they are:

1. between 18 and 74 years of age,
2. have stable coronary artery disease and diabetes mellitus, already on DAPT with aspirin and clopidogrel for at least 6 months,
3. not on any physician-prescribed medications or complementary/alternative therapies,

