#### *Exclusion criteria*

Patients are ineligible to participate if any of the following criteria are met:

1. presence of active internal bleeding or history of bleeding diathesis or clinical findings associated with an increased risk of bleeding,
2. history of ischemic or hemorrhagic stroke, transient ischemic attack, intracranial neoplasm, arteriovenous malformation, or aneurysm,
3. history of clinical and/or hemodynamic instability,
4. within 1 month of placement of a bare metal stent,
5. within 30 days of coronary artery bypass graft surgery or PCI without a stent placed,
6. planned coronary revascularization,
7. treatment with fibrin-specific fibrinolytic therapy <24 h or non-fibrin-specific fibrinolytic therapy <48 h,
8. use of an oral anticoagulation agent or international normalized ratio >1.5,
9. body weight <60 kg,
10. age >75 years,
11. hemoglobin <10 g/dL,
12. platelet count <100×10^6/µL,
13. creatinine >2 mg/dL,
14. hepatic enzymes >2.5 times the upper limit of normal,
15. pregnancy and/or lactation.

The study will undergo a formal approval process by the Campus Ethics Committee (CEC) of the University of the West Indies (UWI) and all patients are to provide written informed consent before participating in the study. The trial will be conducted by the Declaration of Helsinki and the International Conference on Harmonization (ICH) Guidelines for Good Clinical Practice (GCP). Two clinical research associates (CRAs) will secure and assess the quality of the data and the university biostatistician will perform the data analysis after data lock. The CRAs will then deliver the database and the analysis results to the principal investigator (PI). Data will be coded per patient by first letter of first name, first letter of last name followed by numerical date of birth in the order of day, month, and year in a password-protected and encrypted

database program in the office of Lecturer [name] at the Department of Clinical Medicine office, [name], Eric Williams Medical Sciences Complex.

*Patient Interview and Case Report Form*

If a patient satisfies the selection criteria from the initial screening process, a physician or CRA-directed interview will then be administered. Demographic and anthropometric data will be recorded on a case report form (CRF). This will comprise the patient's medical and procedural history including any active medications.

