Each patient will then be allocated via a computerized randomization program. Patients on DAPT for at least 6 months will be tested for platelet function testing with the P2Y12 VerifyNow assay at baseline. The patient will be administered empagliflozin 25 mg once daily for 10 days, followed thereafter by platelet function testing. The study will be randomized via a computer randomization program with a permuted block design and concealment allocation. It is also a controlled, prospective trial design, as group A serves to act as a baseline comparator group and group B has the desired antiplatelet strategy to be investigated over the longitudinal 2-week period. The study will also be blinded as patients will be unaware of their treatment assignments as well as the CRA or physician (Interventional Cardiologist) that performs the platelet function testing.

*Blood Sampling, Phlebotomy*

Blood samples for platelet function testing will be collected at baseline before the patients are administered empagliflozin (baseline sample). Blood will be drawn via an antecubital vein using a 21-gauge needle. The initial 5 mL of all blood samples will be discarded as medical waste as per the institution's policy (to avoid spontaneous platelet activation). Several laboratory tests will be performed including:

1. Complete Blood Count
2. Renal Function Profile
3. Hepatic Function Profile
4. VerifyNow P2Y12 PRU test assay - which will also be performed at the 2nd-week time point after patients have completed their assigned treatment schedules.

Overall, there will be 2 separate instances in which blood sampling/phlebotomy will be performed.

*Aggregation Testing, Platelet Function Testing*

Citrated blood samples are processed by CRAs and study investigators. The platelet function assay to be utilized is the VerifyNow P2Y12 (VN-P2Y12) assay (Accriva, San Diego, California). In brief, the VN-P2Y12 assay is a rapid whole blood point-of-care device that reports results as P2Y12 reaction units (PRU) and percent inhibition of platelet aggregation (%IPA). Assays will be performed as per the instructions of the manufacturer previously described. Please see attached:

- <http://www.accriva.com/uploads/assets/clsi-procedures/14983-revf.docx>
- <http://www.accriva.com/uploads/assets/clsi-procedures/14982-revk.doc>

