**Safety Considerations:**

Overall, patient risk would be considered minimal.

The risks of phlebotomy coupled with treatment and management are:

1. Arterospasm, Hematoma – sterile compression bandage will be done to achieve hemostasis monitoring of vital signs digital pulse oximetry to ensure perfusion of tissues, blood transfusions, Vascular Surgeon consultation for brachial artery repair, and/or luminal dilatation.
2. Nerve damage/injury- Orthopaedic management of possible injury to median nerve, evaluation, and follow-up in the clinic, and possible anti-inflammatory medications for nerve inflammation.
3. Infection- Debridement, microscopy, culture, and sensitivity as well as initiating empirical broad-spectrum antibiotics, and monitoring for signs of sepsis. If febrile or septic shock admission to hospital and commencement of intravenous fluids, intravenous antibiotics with possible ICU intervention.
4. Low risk: Phlebotomy: Vascular spasm, hematoma, local infection, Medium Risk Phlebotomy: nerve damage/injury (unlikely), Empagliflozin: urinary tract infections, fungal infections, (rare-occasional, usually not life-threatening), Serious Risk Phlebotomy: hand surgery (exceedingly rare), Empagliflozin: diabetic ketoacidosis, Fournier's gangrene, and hypoglycemia (very rare).

The study will be by the summary of risks and risk-reduction strategies outlined in Table 8 in the WHO Guidelines on Drawing Blood: Best Practices in Phlebotomy. Any serious adverse events (SAEs) will be recorded as per the Bleeding Academic Research Consortium (BARC) group definitions and reported to the Ethics Committee of the University of the West Indies within 24 hours. The patient will receive health care per the participating institution's guidelines and policies i.e. Cardiology Department at EWMSC, Mt. Hope, Trinidad & Tobago.

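### Two eligibility rules cannot be applied as written: inclusion criterion 3 bars the drugs that criterion 2 requires, and exclusion 12 prints a platelet cut-off that no patient can reach

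*Combined protocol and SAP*

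**What the plan says.** **Background drugs.** Under Inclusion criteria, criterion 2 asks for stable coronary disease and diabetes in patients "already on DAPT with aspirin and clopidogrel for at least 6 months". Criterion 3, the next line, asks that they be "not on any physician-prescribed medications or complementary/alternative therapies". It has no word such as *other* and no exception for aspirin and clopidogrel.

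Three places outside the eligibility list describe the population as patients on dual antiplatelet therapy (DAPT):
- Null Hypothesis: "There is no difference in response in patients with stable coronary artery disease on DAPT concerning PRUs on Empagliflozin".
- Study Goals and Objectives: "To describe platelet function profiles of patients with stable coronary artery disease on DAPT on Empagliflozin".
- The allocation and baseline-testing paragraph, after Patient Interview and Case Report Form: "Patients on DAPT for at least 6 months will be tested for platelet function testing".

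**Platelet count.** Under Exclusion criteria, item 12 reads "platelet count <100×10 6 /µL", where the 6 is a superscript exponent. The list opens with the rule "Patients are ineligible to participate if any of the following criteria are met", so meeting one item is enough to bar a patient.

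**The concern.** Both lines are operative rules that decide who may enter the trial, and each appears to leave nobody eligible if followed to the letter.

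For criterion 3, staff can see that DAPT patients are meant to be enrolled, but they can enrol them only against the printed text. Reading in the word *other* does not settle the matter. Patients with diabetes and coronary disease may be taking prescribed drugs for those conditions, and the plan does not say whether that bars them. The answer decides which patients the result describes, in a study of at least 16 patients (Data Management and Statistical Analysis) or 20 (Sample Size Calculation).

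For exclusion 12, the stake is the low-platelet safety screen, which has no usable written value. All patients take two antiplatelet drugs, and the hypothesis is that empagliflozin lowers platelet reactivity further. The plan itself treats bleeding as a concern: exclusion 1 covers bleeding risk, and Safety Considerations states "Any serious adverse events (SAEs) will be recorded as per the Bleeding Academic Research Consortium (BARC) group definitions".

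**Working it through.** The plan gives no derived figure to reproduce here. The check is a logical comparison for the first rule and unit arithmetic for the second.

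**Step 1. Criterion 2 against criterion 3.**
- Input: criterion 2 requires current aspirin and clopidogrel.
- Input: criterion 3 requires no physician-prescribed medication.
- Assumption: clopidogrel is physician-prescribed. The plan does not say so.
- Result: a patient who meets criterion 2 is on a prescribed drug and so fails criterion 3. Patients who meet both = 0.

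**Step 2. Does other text repair criterion 3?**
- The null hypothesis, the objective and the baseline-testing paragraph all place the patients on DAPT. This shows the intent but does not amend the criterion.
- Exclusion 8 separately bars oral anticoagulants. A ban on all prescribed drugs would already cover any that are prescribed.
- The case report form records active medications for patients who have already passed selection.
- The last two points suggest that some background drugs may be expected. They do not say which, so the scope of criterion 3 stays open.

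**Step 3. Exclusion 12 in plain units.**
- 100 × 10⁶/µL = 100,000,000/µL, or 1 × 10¹⁴ per litre.
- A patient would need at least 100,000,000 platelets/µL to escape this exclusion.

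**Step 4. Comparison with plausible counts.** The counts below are assumptions; the documents give none.

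| Assumed count per µL | Printed cut-off ÷ count |
|---|---|
| 150,000 | 100,000,000 / 150,000 = 666.7 |
| 450,000 | 100,000,000 / 450,000 = 222.2 |
| 1,000,000 (extreme) | 100 |
| 2,000,000 (more extreme) | 50 |

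**Step 5. Physical check.** Assume a mean platelet volume of 7 to 12 fL, and note that 1 µL = 10⁹ fL.
- 100,000,000 × 7 / 10⁹ = 0.70
- 100,000,000 × 12 / 10⁹ = 1.20

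Platelets alone would fill 70% to 120% of the blood volume, so no patient could reach the cut-off.

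**Step 6. Nature of the slip.** The same digits per mL, or an exponent of 3 in place of 6 per µL, would each give 100,000/µL. The pattern fits a 1000-fold error in unit or exponent. That indicates what to check; it is not a proposal for the right threshold.

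**Step 7. Effect of the any-one rule.** Every patient falls below the printed cut-off and one exclusion suffices, so item 12 alone excludes everyone.

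Nothing here depends on the significance level, power, standard deviation or sample size.

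**The case against.** The strongest reply is that nobody would apply either line literally. Criterion 2 is specific and sits directly above criterion 3, the rest of the plan describes patients on DAPT, and the separate anticoagulant exclusion would be largely redundant under a total ban. Read as a whole, criterion 3 means no *other* medications, so the fault is a missing qualifier and zero enrolment is not a real outcome. **This stands in part.** The intent to enrol DAPT patients is evident and the practical harm is lower than the literal reading suggests. But the *no other* reading would bar every other prescribed drug in patients with diabetes and coronary disease, and the plan does not confirm that this is meant.

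A second reply is that text may have been lost when the PDF was read. Criterion 3 ends in a comma with nothing after it, and exclusion 12 turns on a single exponent or unit symbol. **This cannot be ruled out entirely.** However, no gap or redaction is marked at criterion 3, and the superscript and unit in exclusion 12 appear intact. A check against the source file answers the point.

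A third reply is that an impossible cut-off would be noticed at the first screening, that it errs towards exclusion, and that exclusions 1 and 8 also screen for bleeding risk through clinical findings and the international normalized ratio. **All true, but none of these supplies a platelet threshold.** Once staff set the printed value aside, they must choose their own.

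Finally, neither error alters the planned analysis or the sample size. That is correct. The defect lies in who may be enrolled.

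**Conclusion.** The concern holds. Both lines are wrong as written and should be corrected before enrolment; neither is a matter of design preference.

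- **Criteria 2 and 3:** read literally, 0 eligible patients, assuming clopidogrel is physician-prescribed. Evident intent softens this, but the rule on other background drugs remains undefined.
- **Exclusion 12:** the printed cut-off is about 222 to 667 times an assumed count of 450,000 down to 150,000/µL, and still 50 times an assumed extreme of 2,000,000/µL. The conclusion does not turn on the exact range.

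The contradiction and the arithmetic are certain for the text as printed here. Whether the exponent or unit is also wrong in the sponsor's source file is likely but needs checking. The figures describe the literal reading, not expected recruitment.

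**What to change.** 1. Reconcile inclusion criteria 2 and 3 so that the required aspirin and clopidogrel do not breach criterion 3.
2. State in the same amendment what is intended for other prescribed drugs and for complementary or alternative therapies, so that staff need not infer it.
3. Verify the exponent and unit of exclusion 12 against the source and correct the printed value.

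Which medications are permitted and what platelet threshold applies are for the sponsor to decide; neither is suggested here.

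The cost is protocol wording only, with no change to the sample size, assay, visits or analysis. While making the change, the sponsor could also confirm that the platelet count and medication history are in hand before eligibility is decided. The blood count is listed with the baseline samples, and the medication history is taken after selection criteria are met. This is a request for confirmation, not a further defect.

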#### *Exclusion criteria*

Patients are ineligible to participate if any of the following criteria are met:

1. presence of active internal bleeding or history of bleeding diathesis or clinical findings associated with an increased risk of bleeding,
2. history of ischemic or hemorrhagic stroke, transient ischemic attack, intracranial neoplasm, arteriovenous malformation, or aneurysm,
3. history of clinical and/or hemodynamic instability,
4. within 1 month of placement of a bare metal stent,
5. within 30 days of coronary artery bypass graft surgery or PCI without a stent placed,
6. planned coronary revascularization,
7. treatment with fibrin-specific fibrinolytic therapy <24 h or non-fibrin-specific fibrinolytic therapy <48 h,
8. use of an oral anticoagulation agent or international normalized ratio >1.5,
9. body weight <60 kg,
10. age >75 years,
11. hemoglobin <10 g/dL,
12. platelet count <100×10^6/µL,
13. creatinine >2 mg/dL,
14. hepatic enzymes >2.5 times the upper limit of normal,
15. pregnancy and/or lactation.

The study will undergo a formal approval process by the Campus Ethics Committee (CEC) of the University of the West Indies (UWI) and all patients are to provide written informed consent before participating in the study. The trial will be conducted by the Declaration of Helsinki and the International Conference on Harmonization (ICH) Guidelines for Good Clinical Practice (GCP). Two clinical research associates (CRAs) will secure and assess the quality of the data and the university biostatistician will perform the data analysis after data lock. The CRAs will then deliver the database and the analysis results to the principal investigator (PI). Data will be coded per patient by first letter of first name, first letter of last name followed by numerical date of birth in the order of day, month, and year in a password-protected and encrypted

database program in the office of Lecturer [name] at the Department of Clinical Medicine office, [name], Eric Williams Medical Sciences Complex.

*Patient Interview and Case Report Form*

If a patient satisfies the selection criteria from the initial screening process, a physician or CRA-directed interview will then be administered. Demographic and anthropometric data will be recorded on a case report form (CRF). This will comprise the patient's medical and procedural history including any active medications.

Each patient will then be allocated via a computerized randomization program. Patients on DAPT for at least 6 months will be tested for platelet function testing with the P2Y12 VerifyNow assay at baseline. The patient will be administered empagliflozin 25 mg once daily for 10 days, followed thereafter by platelet function testing. The study will be randomized via a computer randomization program with a permuted block design and concealment allocation. It is also a controlled, prospective trial design, as group A serves to act as a baseline comparator group and group B has the desired antiplatelet strategy to be investigated over the longitudinal 2-week period. The study will also be blinded as patients will be unaware of their treatment assignments as well as the CRA or physician (Interventional Cardiologist) that performs the platelet function testing.

*Blood Sampling, Phlebotomy*

Blood samples for platelet function testing will be collected at baseline before the patients are administered empagliflozin (baseline sample). Blood will be drawn via an antecubital vein using a 21-gauge needle. The initial 5 mL of all blood samples will be discarded as medical waste as per the institution's policy (to avoid spontaneous platelet activation). Several laboratory tests will be performed including:

1. Complete Blood Count
2. Renal Function Profile
3. Hepatic Function Profile
4. VerifyNow P2Y12 PRU test assay - which will also be performed at the 2nd-week time point after patients have completed their assigned treatment schedules.

Overall, there will be 2 separate instances in which blood sampling/phlebotomy will be performed.

*Aggregation Testing, Platelet Function Testing*

Citrated blood samples are processed by CRAs and study investigators. The platelet function assay to be utilized is the VerifyNow P2Y12 (VN-P2Y12) assay (Accriva, San Diego, California). In brief, the VN-P2Y12 assay is a rapid whole blood point-of-care device that reports results as P2Y12 reaction units (PRU) and percent inhibition of platelet aggregation (%IPA). Assays will be performed as per the instructions of the manufacturer previously described. Please see attached:

- <http://www.accriva.com/uploads/assets/clsi-procedures/14983-revf.docx>
- <http://www.accriva.com/uploads/assets/clsi-procedures/14982-revk.doc>

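### The supplied text calls the study both open-label and patient-blinded, and claims randomisation with a comparator group A without saying what that group receives, so no single design or primary comparison can be identified

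*Combined protocol and SAP*

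**What the plan says.** - **Study Design:** "The study will be a prospective, open-label study that aims to assess the effect of empagliflozin". No second group is mentioned.
- **Methodology, allocation paragraph (after Patient Interview and Case Report Form):** "The study will be randomized via a computer randomization program with a permuted block design and concealment allocation". The design is also called controlled, in that "group A serves to act as a baseline comparator group and group B has the desired antiplatelet strategy". On masking: "The study will also be blinded as patients will be unaware of their treatment assignments"; the same is said of whoever performs the platelet function test. On treatment: "The patient will be administered empagliflozin 25 mg once daily for 10 days, followed thereafter by platelet function testing".
- **Blood Sampling, Phlebotomy:** "Blood samples for platelet function testing will be collected at baseline before the patients are administered empagliflozin". The second assay is placed at the second-week "time point after patients have completed their assigned treatment schedules".
- **Null Hypothesis:** "There is no difference in response in patients with stable coronary artery disease on DAPT concerning PRUs on Empagliflozin". The single entry under Study Goals and Objectives is descriptive and also concerns only patients taking empagliflozin.
- **Data Management and Statistical Analysis:** a Student's t-test, not stated to be paired or independent; no primary comparison; least-square means promised with no model named; a target of 16 or more patients.
- **Sample Size Calculation:** inhibition of about 50% moving to 55%, type 1 error 5%, power 80%, n = 20. The calculator link has the word parallel in its file name. No SD is given, and 20 is not identified as a total or a per-group number.
- **Budget:** 25 sets of consent and case report forms.

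**The concern.** The sections describe designs that cannot all be the same study. A patient who knows the treatment is not blinded to it, so the open-label label and the patient-blinding claim exclude each other. Separately, randomisation and concealment need at least two assignments, but only one treatment is described and it is given to patients in general.

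What is at stake is the quantity the trial estimates. A within-patient change in one group contains the drug effect plus anything else that shifts PRU between the two samples, such as regression to the mean or assay variation. A between-group difference removes what is common to both groups. The two need different tests and different SDs for the sample size, and they support different claims. If the choice is left open until data are in hand, the primary result is open to selection. If the study turns out to have one group, calling it randomised, controlled and blinded would misstate the evidence.

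**Working it through.** **1. Each stated property under each reading**

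| Statement | One group, all treated | Two groups, patients masked | Two groups, patients not masked |
|---|---|---|---|
| Open-label (Study Design) | holds | fails | holds |
| Patients unaware of assignment (Methodology) | fails: there is no assignment | holds, method not described | fails |
| Permuted blocks, concealed allocation (Methodology) | fails | holds | holds |
| Controlled, groups A and B (Methodology) | only as the patients' own baseline; no concurrent control | concurrent; group A's treatment not stated | concurrent; group A's treatment not stated |
| Empagliflozin given to the patient, unrestricted (Methodology) | holds | must be limited to group B | must be limited to group B |

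No column is free of a failure.

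**2. Can intent be read from the rest of the text?** The null hypothesis, the objective and the unrestricted treatment sentence point to one group. The reference to assigned schedules, the group A/B sentence and the name of the calculator link point to two. The comparator phrase fits either. The analysis section does not break the tie: an unqualified t-test serves both readings, and least-square means require a fitted model that is not named.

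**3. Does n = 20 show which design was meant?** Inputs from Sample Size Calculation: difference 55 − 50 = 5 points, alpha 5% (two-sided assumed), power 80%. In the normal approximation, (1.96 + 0.84)² is about 7.85.

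- Parallel groups: n per group = 2 × 7.85 × SD² / 5² = 0.628 × SD², where SD is that of the outcome compared.
- One group, paired: n = 7.85 × SD² / 5² = 0.314 × SD², where SD is that of the within-patient change.

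Neither SD is in the documents, so n = 20 can be neither reproduced nor refuted, and it does not identify the design. The assumption is also in percent inhibition, while the null hypothesis is in PRU, and no conversion is given.

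**4. Is 20 a total or a per-group number?** Compare with the 25 form sets in Budget:

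- 20 per group: 2 × 20 = 40, more than 25.
- 16 per group: 2 × 16 = 32, more than 25.
- One group of 20, or two of 10 (2 × 10 = 20): both fit within 25.
- One group of 16, or two of 8 (2 × 8 = 16): both fit within 25.

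The budget therefore suggests that 20 (or 16) is a total. It does not separate one group of 20 from two groups of 10.

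**The case against.** The strongest reply is that this is a small before/after study in which patients are their own controls, group A is simply the baseline measurement, and the other design terms are loose wording. On that reading the repair is mostly deletion. This is plausible, and self-control is a legitimate form of control; only a concurrent control would be missing. But the randomisation, concealment and patient-blinding statements would then be false as they stand. A reader might infer that the trial certainly is single-group and has been mislabelled. The documents do not support that either, given the assigned schedules, the two named groups and the calculator's name.

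A second reply is that open-label trials are often randomised, with concealed allocation and a masked assay reader. That stands: open-label does not contradict any of those. The contradiction lies in the patient-blinding claim alone.

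Third, parts of the document were not available, and the Informed Consent Forms section points to a separate file. So the statements that group A's treatment and the masking method are missing apply to the supplied text only. The conflict between Study Design and Methodology does not depend on what is absent.

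Two further inferences should be resisted. A reader might conclude that the trial is underpowered. With no SD in the documents, any figure would be solved backwards from n, and on an inhibition scale rather than in PRU. A reader might also take the Project Management table, which lists both research associates for consent, sampling and assay, as proof that assay masking fails. The table does not show that.

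**Conclusion.** The point holds on the text. Under every reading at least one stated design property is false: with one group, randomisation, concealment, concurrent control and patient blinding; with two groups, either open-label or patient blinding, and group A is undefined as well. The primary contrast cannot be identified from the objectives, the analysis section or the sample size.

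The size is not a number. No power shortfall is claimed, because none can be calculated without an SD. That 20 is a total is an inference from the 25 form sets, not a statement in the plan. Which design was intended is left open. The conclusion assumes only that the supplied sections are current and are meant to describe one study. It needs to be resolved before the data are analysed, since the test and the permissible claim both depend on it.

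**What to change.** Reconcile Null Hypothesis, Study Goals and Objectives, Study Design, the allocation and sampling text in Methodology, Data Management and Statistical Analysis, and Sample Size Calculation to one design.

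**(a) If every patient receives empagliflozin:** call it a single-group, open-label, before/after study. Delete the randomisation, concealment, group A/B and patient-blinding statements. Make the within-patient change in PRU, by paired t-test, the primary analysis. Name a model for the least-square means or remove them. Do not present the result as randomised, controlled evidence.

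**(b) If group A is concurrent:** state what it receives and that it is assayed at the same two times. Limit the empagliflozin sentence to group B. Either describe the masking and correct Study Design, or drop the patient-blinding claim. Make the between-group difference in PRU, adjusted for baseline PRU, the primary comparison; that model also supplies the least-square means.

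**In either case:** restate the sample-size basis for the chosen design: total or per group, the SD used and its scale, which of 16 and 20 applies, and the resulting power.

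**Cost:** protocol wording and one named primary comparison. Under (a), the claim becomes more modest. Under (b), the stated power for the same total may be lower, depending on the SD.
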